4.2. Study Design Rationale

Crossover designs are a well-established study design in which subjects are exposed to multiple treatments during different time periods. This design was considered since the study period is relatively short the design can be cost effective and more efficient comparisons between treatments can be made than compared a parallel study since fewer subjects are required to achieve the same pre-specified statistical power. [REDACTED]

[REDACTED] significant carryover effects were observed when assessing clinically relevant differences between the Test lens and a comparator while using a 2×2 crossover study design. Therefore this study utilizes a 3-period

by 2-treatment in order to estimate the true effect of the Test lens without any potential bias from the carry-over effect.

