5. TEST ARTICLE ALLOCATION AND MASKING

5.1. Test Article Allocation

This is a multi-site, partially-subject masked (control lens only) and randomized study. The study lenses will be worn in a bilateral and random fashion using a 2 treatment by 3 period (2×3) crossover design.

Permuted block randomization will be used to minimize the potential for treatment imbalance. A block size of two (2) sequences will be utilized. A computer-generated randomization scheme will be used to randomly assign subjects to one of the two possible lens wear sequences (TEST/CONTROL/CONTROL or CONTROL/TEST/TEST). The random scheme will be generated using the PROC PLAN procedure from SAS Software Version 9.4 or higher (SAS Institute, Cary, NC).

The study site must follow the randomization scheme provided and complete enrollment according to the randomization list and not pre-select or assign subjects. The randomized assignment of subjects will be performed at the first visit prior to the first fitting. The following must have occurred prior to randomization:

- Informed consent has been obtained
- Subject meets all the inclusion / exclusion criteria
- Subject history and baseline information has been collected

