14.5. Primary Analysis

Primary efficacy analysis:

Visual Acuity

Distance monocular visual acuity (logMAR) will be analyzed using a Bayesian multivariate normal random-effects model to compare the Test and control lenses. The regression model will include sequence of lens wear, lens type and first-order carryover effect as fixed effects. Clinical site and subject nested within clinical site will be included as random effects. Other subject characteristics such as gender and age will be included as fixed effects when appropriate.

The Model:

Let $y_{ijklm} = (y_{1ijklm}, y_{2ijklm}, y_{3ijklm})$ denote the visual acuity (logMAR) for the m^{th} subject at the l^{th} site, assigned to the i^{th} lens for the j^{th} eye using the k^{th} sequence at periods 1, 2, 3, respectively. The likelihood for y_{ijkl} is constructed as follows:

$$y_{ijklm} \sim \mathcal{N}(\mu_{ijklm}, \Sigma)$$

Where $\mu_{ijklm} = (\mu 1_{ijklm}, \mu 2_{ijklm}, \mu 3_{ijklm})^T$ and Σ is a 3X3 variance-covariance matrix. Here,

$$\mu_{1ijklm} = \mu_0 + \pi_1 + \beta_1 \text{Lens}_{i[j,k]} + \beta_4 \text{Sequence}_k + \gamma_l + \delta_{l(m)} + \alpha_{j(m(l))}$$

$$\mu_{2ijklm} = \mu_0 + \pi_2 + \beta_2 \text{Lens}_{i[j,k]} - \beta_4 \text{Sequence}_k + \beta_5 \text{Carry1}_{i[j,k]} + \gamma_l + \delta_{l(m)} + \alpha_{j(m(l))}$$

$$\mu_{ijklm} = \mu_0 + \pi_3 + \beta_3 \text{Lens}_{i[j,k]} + \beta_4 \text{Sequence}_k - \beta_5 \text{Carry1}_{i[j,k]} + \gamma_l + \delta_{l(m)} + \alpha_{j(m(l))}$$

In this model π_1, π_2, π_3 represent the effect of period with the constraint $\pi_1 + \pi_2 + \pi_3 = 0$. In Lens I will be determined by the subject eye j and sequence k, therefore i is denoted as a function of j and k. We define $\text{Lens}_i=0$ for the control lens and $\text{Lens}_i=1$ for the Test lens, sequence is defined as: Sequence=0 for the order Control/Test/Test and Sequence=1 for order Test/Control/Control. The first-order carryover effect will be defined as carry=0 for the Control lens and carry=1 for the Test lens. So β_1 stands for the difference between the Test and control lens with respect to visual performance at period 1. A negative β_2 indicates the Test performed better than the control lens.

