We assume random subject eye effects are independent and identically distributed (i.i.d) as $\alpha_{j(m(l))} \sim N(0, \sigma_{\text{eye/subject/site}}^2)$ as random eye nested within subject within clinical site, the random subject effect are i.i.d as $\delta_{l(m)} \sim (0, \sigma_{\text{subject/site}}^2)$ as random subject nested within clinical site and the random site effect is i.i.d as $\gamma_l \sim N(0, \sigma_{\text{site}}^2)$ for $i=1,2$ (lens), $j=1, 2$ (eye), $k=1, 2$ (sequence), $\text{carry1}=1, 2$ (first-order carryover effect) and $l=1 \dots |m_l(\text{subject/site})|$ and $l=1, 2, 3, 4$ and 5 (site).

For the β coefficients, independent non-informative priors $N(0, 1000)$ will be used. For the variance of random effects $\sigma_{\text{eye/subject/site}}^2$, $\sigma_{\text{subject/site}}^2$ and σ_{site}^2 independent non-informative conjugate priors inverse-gamma(0.001, 0.001) will be used. For Σ , non-informative conjugate priors inverse-wishart(3,S) will be used where S is a 3X3 variance-covariance matrix of y_{ijklm} . The metropolis sampler algorithm as implemented in the SAS/STAT MCMC procedure will be used to estimate the posterior distribution of the unknown parameters. Inferences will be made based on the 95% posterior credible intervals for relevant parameters.

Hypothesis Testing

The null and alternative hypothesis for visual acuity (logMAR) to test for non-inferiority of the Test lens relative to the control lens is as follows:

$$H_0: \frac{\beta_1 + \beta_2 + \beta_3}{3} \geq 0.05$$

$$H_A: \frac{\beta_1 + \beta_2 + \beta_3}{3} < 0.05$$

Non-inferiority will be declared if the upper limit of the 95% credible interval of the difference between the Test and Control is below 0.05, i.e. $P(\frac{\beta_1 + \beta_2 + \beta_3}{3} < 0.05) \geq 0.975$. Superiority will be established if the upper limit of the 95% credible interval of the difference between the Test and Control lens is below 0.0, i.e. $P(\frac{\beta_1 + \beta_2 + \beta_3}{3} < 0.0) \geq 0.975$. Superiority will be tested only if non-inferiority is met.

CLUE Overall Comfort

CLUE Comfort scores will be analyzed using a Bayesian multivariate normal random-effects model to compare the Test and control lenses. The regression model will include baseline CLUE comfort scores, sequence of lens wear, lens type and first-order carryover as fixed

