For the β coefficients, independent non-informative priors $N(0, 1000)$ will be used. For the variance of random effect of σ_{site}^2 an independent non-informative conjugate prior, inverse-gamma(0.001, 0.001) will be used. For Σ , non-informative conjugate priors inverse-wishart(3,S) will be used where S is a 3X3 variance-covariance matrix of y_{ijkl} . Starting values for the mean and variance of CLUE scores will be 60 and 400 (since standard deviation of CLUE is normalized to be 20), respectively. The Metropolis sampler algorithm as implemented in the SAS/STAT MCMC procedure will be used to estimate the posterior distribution of the unknown parameters. Inferences will be made based on the 95% posterior credible intervals for relevant parameters.

Hypothesis Testing

The null and alternative hypotheses for CLUE comfort non-inferiority of the Test lens relative to the control lens are as follows:

$$H_o: \frac{\beta_1 + \beta_2 + \beta_3}{3} \leq -5$$

$$H_A: \frac{\beta_1 + \beta_2 + \beta_3}{3} > -5$$

Non-inferiority will be declared if the lower bound of the 2-sided 95% credible interval of the difference between the Test lens and the control lens is greater than -5, i.e., $P(\frac{\beta_1 + \beta_2 + \beta_3}{3} > -5) \geq 0.975$. Superiority will be declared if the lower bound of the 2-sided 95% credible interval of the difference between the Test and Control lens is greater than 0, i.e., $P(\frac{\beta_1 + \beta_2 + \beta_3}{3} > 0) \geq 0.975$. Superiority will only be tested if non-inferiority is established.

Lens Fit Acceptance

Lens fit acceptance will be analyzed using a Bayesian Logistic regression random-effects model to estimate the proportion of subjects eyes wearing the Test lens having acceptable lens fitting. The regression model will include period, sequence of lens wear and first order carryover effect. Site, subject nested within site and eye within subject within site will be included in the model as random effects.

Let $y_{ijklm}=1$ if an acceptable lens fit is observed for eyes wearing the Test lens only and $y_{ijklm}=0$ otherwise for the m^{th} subject, from the l^{th} site, for the i^{th} eye in the j^{th} period using the k^{th} sequence.

$$Y_{ijklm} \sim \text{Binary } (p_{ijklm})$$

$$p_{ijklm} = \frac{\exp(\text{Numerator})}{1 + \exp(\text{Numerator})}$$

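### The CLUE and visual-acuity models have eight mean parameters for six cell means, so the tested lens effect is not identifiable and, at the planned zero difference, non-inferiority cannot be declared at any sample size

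*Combined protocol and SAP*

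**What the plan says.** Section 5.1 randomises subjects to one of two sequences, "TEST/CONTROL/CONTROL or CONTROL/TEST/TEST", in equal numbers ("A block size of two (2) sequences will be utilized").

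For visual acuity, the prose of section 14.5 reads: "The regression model will include sequence of lens wear, lens type and first-order carryover effect as fixed effects". The displayed mean equations contain more than that:

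- an intercept μ0;
- three period terms, which "represent the effect of period with the constraint" that they sum to zero;
- a separate lens coefficient in each period, where β1 "stands for the difference between the Test and control lens with respect to visual performance at period 1";
- a sequence coefficient entered as +, −, + over the three periods;
- a carryover coefficient entered as + in period 2 and − in period 3.

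The test is on (β1+β2+β3)/3: "Non-inferiority will be declared if the upper limit of the 95% credible interval of the difference between the Test and Control is below 0.05". For the coefficients, "independent non-informative priors $N(0, 1000)$ will be used".

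CLUE Comfort has the same equations plus a baseline slope, the same prior, and a margin of −5 points on the same average. Section 14.6 applies the CLUE analysis to Vision and Handling. Section 2.3 requires every primary and secondary hypothesis to be met. Section 4.2 says the third period was added "in order to estimate the true effect of the Test lens without any potential bias from the carry-over effect".

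**The concern.** Six cell means cannot support eight mean parameters. Over-parameterisation does no harm if the tested quantity is still estimable, so the question is whether the average lens effect can be separated from the sequence and carryover terms. If it cannot, its credible interval reflects the priors and does not shrink as subjects are added.

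That would affect visual acuity, CLUE Comfort, CLUE Vision and CLUE Handling. It would also mean that the model gives up the carryover protection for which the third period was added. Whoever programs the analysis would have to report an uninformative interval or choose a new primary model, possibly after seeing data.

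**Working it through.** **Inputs.** Two sequences, TCC and CTT, allocated 1:1 (5.1). CLUE variance 202 and covariance 105, true difference 0 (14.2). Logmar SD 0.10 and between-eye correlation 0.80 (14.2). Prior N(0, 1000), read as variance 1000 (14.5). Target of 120 completers (synopsis). No prior is printed for μ0 or the period effects, so they are taken as flat.

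**1. The plan's own figure.** Table 7 gives 80% power for CLUE Comfort at 60 completers. Section 14.2 obtained it from a different model: lens, period and lens × period, with no sequence or carryover term. That model has six parameters for six means. The per-subject contrast (y1−y2−y3)/3 has variance (3×202 − 2×105)/9 = 44, so SE = √(44×4/60) = 1.713. With margin 5 and 58 df, power is 81.9%. The stated 80% is reproduced to within 2 points.

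**2. Parameter count in 14.5.** μ0 (1) + period (2 free) + lens (3) + sequence (1) + carryover (1) = 8. The CLUE baseline slope is extra and is identified separately. The 6×8 design matrix has rank 6. Appending the tested contrast raises the rank to 7, so the contrast is not estimable.

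**3. What the data determine.** Let Dp be the TCC minus CTT mean in period p, with Carry = 1 if the preceding lens was Test:

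- D1 = β1 + βseq
- D2 = −β2 − βseq + βcarry
- D3 = −β3 + βseq + βcarry

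Hence (β1+β2+β3)/3 = (D1 − D2 − D3 − βseq + 2βcarry)/3. No other contrast supplies βseq or βcarry.

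**4. Limiting posterior.** In the order (β1, β2, β3, βseq, βcarry), the directions that leave every D unchanged are u = (−1, −1, 1, 1, 0), squared length 4, and v = (0, 1, 1, 0, 1), squared length 3. They are orthogonal. The target has inner product −1/3 with u and 2/3 with v. The limiting variance is therefore 1000×[(1/9)/4 + (4/9)/3] = 1000×(1/36 + 4/27) = 175.9. The SD is 13.26 and the 95% half-width is 1.96×13.26 = 26.0.

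**5. Finite samples.** The CLUE posterior SD is 13.29 at n=60, 13.28 at n=120 and 13.26 at n=120,000. For logMAR it is 13.26 at n=40 and at n=120. With the posterior centred at zero, P(effect > −5) = Φ(5/13.28) = 0.65 for CLUE, and P(effect < 0.05) = Φ(0.05/13.26) = 0.50 for visual acuity. The rule needs 0.975.

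**6. Other readings, keeping three lens coefficients.** All have rank 6, and 7 with the target appended.

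| Carryover code | Signs | SD, n=120 | Limiting SD | Limiting half-width |
|---|---|---|---|---|
| preceding lens | as printed | 13.28 | 13.26 | 26.0 |
| preceding lens | all + | 5.36 | 5.27 | 10.3 |
| fixed by sequence | as printed | 6.58 | 6.46 | 12.7 |
| fixed by sequence | all + | 12.38 | 12.36 | 24.2 |

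At a true difference of 0, the chance of declaring CLUE non-inferiority is below 0.003% at n=60 in every row and falls as n grows. Dropping carryover but keeping sequence is still not estimable.

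**7. Models that work, and one that does not.**

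- *One lens coefficient β, constant signs.* D1 = β+s, D2 = −β+s+c, D3 = −β+s−c, so β = (2D1−D2−D3)/4, with rank 6 of 6. CLUE variance per subject is (6×202 − 6×105)/16 = 36.4, so SE at 120 is √(36.4×4/120) = 1.10. Power is 88.4% at 60 and 99.5% at 120. For logMAR, the two-eye mean has variance 0.01×(1+0.8)/2 = 0.009. The between-period correlation r is not given. SE at 120 is √(0.009×(1−r)×(6/16)×4/120), which is 0.0058 at an assumed r = 0.7 and runs from 0.0106 (r=0) to 0.0034 (r=0.9).
- *Three lens coefficients, no sequence or carryover term.* The estimate is (D1−D2−D3)/3. Ordinary carryover adds +c to D2 and −c to D3 and cancels. A constant sequence effect s leaves a bias of −s/3. SE at 120 is √(44×4/120) = 1.21. Power is 81.9% at 60 and 98.4% at 120.
- *One lens coefficient, printed signs, preceding-lens code.* The estimate is D1 + D2/2 − D3/2, so an ordinary carryover c enters the lens effect in full: 2 points of carryover are reported as a 2-point lens effect. Power is 22% at 60 and 40% at 120.

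**The case against.** The priors are proper, so a posterior exists and failure is not a mathematical certainty for every possible effect. This stands, but it helps little. As printed, CLUE would need a true benefit of about 44 points on a scale with SD 20. Under the kindest alternative reading, about 6 points would suffice. Visual acuity has no escape: even a half-width of 10.3 logMAR is far beyond any real effect, and section 2.3 requires every hypothesis to be met.

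The figure of 13.3 depends on the reading. This also stands. The SD runs from about 5.3 to 13.3, and placing the same N(0, 1000) prior on μ0 and the period effects narrows the interval somewhat. No reading that keeps three lens coefficients and a sequence term brings it inside the margin. If 1000 is an SD, the interval is far wider.

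The minus sign on carryover can be defended if Carry1 is fixed by sequence. On that reading, with one lens coefficient, carryover does not bias the lens effect. The bias in step 7 therefore applies to the preceding-lens code. The alternating sequence sign remains unexplained, and the non-identifiability does not depend on it.

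Section 14.3 lets a separate SAP supersede this section, and section 14.10 allows documented changes. No such SAP is in the text supplied. A later correction would be an unplanned choice of primary model, which is the harm to avoid.

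Finally, the prose sentence describes an estimable model with a single lens effect. That is fair: the fault is in the equations and the averaged hypothesis, which disagree with the prose.

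**Conclusion.** The concern holds. As printed, the tested lens effect for visual acuity and the three CLUE scores is not identifiable. Its interval half-width is about 26 (about 10 under the kindest reading) at any sample size, against margins of 0.05 logMAR and 5 points. At the planned zero difference, non-inferiority cannot be declared.

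The rank result needs only the two sequences and the printed equations. The SDs also assume a prior variance of 1000, flat priors on μ0 and the period effects, and a known covariance. Random effects and the baseline covariate add no between-sequence information. Table 7's CLUE power describes the planning model and not the analysis in 14.5. This must be fixed before the analysis is run.

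**What to change.** In the three mean equations for visual acuity and for CLUE in section 14.5:

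- replace β1, β2 and β3 by one coefficient β on the lens worn in that period;
- enter Sequence with the same sign in all three periods;
- define Carry as 1 if the preceding-period lens was Test, and enter it with a plus sign in periods 2 and 3;
- restate the hypotheses and decision rules in terms of β, against 0.05 logMAR and −5 points, and correct the sentences that interpret the coefficients.

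Report the lens-by-period model without sequence and carryover as supportive. It matches the planning model, is estimable and cancels first-order carryover, but it is exposed to a sequence effect. The single-coefficient model assumes that the lens effect is the same in every period and weights the between-sequence differences (2, −1, −1)/4. The text should say so.

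State whether 1000 is a variance, give priors for μ0 and the period effects, and restate the Table 7 power for the model actually used. If a separate SAP exists, check it for the same equations.

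The cost is a revision of two model specifications and their hypotheses, with no added subjects or data. It should be dated before database lock and before anyone sees results by lens. Masking is not a sufficient safeguard, because section 5.2 says complete masking is impossible.

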2.3. Hypotheses

Primary Hypotheses

All primary and secondary hypotheses must be met in order to satisfy the objective the study.

Primary Hypotheses	
Endpoint	Hypothesis
Monocular logMAR visual acuity	The Test lens will be non-inferior to the control lens with respect to Distance Monocular logMAR Visual Acuity at the 2-week follow-up evaluation. A non-inferiority margin of 0.05 logMAR and a superiority margin of 0 logMAR will be used.
Biomicroscopy	The Test lens will be non-inferior to the control lens with respect

	to the percentage of eyes with Grade 3 or higher Slit Lamp Findings (Biomicroscopy) across all follow-up visits (scheduled and unscheduled). A non-inferiority margin of 5% will be used.
Fit acceptance rate	The proportion of eyes with acceptable fit will be greater than 90% across all scheduled visits for all subjects wearing the Test lens. The fit acceptance rate of the control lens is not a primary endpoint.
Overall CLUE comfort	The Test lens will be non-inferior to the control lens with respect to CLUE Overall Comfort at the 2-week follow-up evaluation. A non-inferiority margin of -5 points will be used

Secondary Hypotheses

Secondary Hypotheses	
Endpoint	Hypothesis
Overall CLUE Vision	The Test lens will be non-inferior to the control lens with respect to CLUE Overall quality of vision at the 2-week follow-up evaluation. A non-inferiority margin of -5 points will be used.
Overall CLUE handling	The Test lens will be non-inferior to the control with respect to CLUE Handling at the 2-week follow-up evaluation. A non-inferiority margin of -5 points will be used.

Other Hypotheses

Other Observations	
Endpoint	Hypothesis
Lens Preferences	The Test lens will be superior to the control lens in all 5 of the following lens preference items at the 2-week follow-up evaluation of the second wearing period. 

Other Observations	
Endpoint	Hypothesis
Indoor Performance Measures	
The Test lens will be superior to the control lens in at least 2 of the following 4 indoor performance measure(s) at the 2-week follow-up evaluation.
 
Driving Performance Metrics	
The Test lens will be non-inferior to the control lens in both of the following driving performance metrics at the 2-week follow-up evaluation. A cumulative odds ratio margin of 0.67 will be used.
 
Outdoor Performance Measures	
The Test lens will be superior to the control lens in at least 2 of the following 4 outdoor performance measure(s) at the 2-week follow-up evaluation.
 

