The sample size calculation for distance monocular visual performance was performed assuming that there was no difference between the Test and Control lenses to achieve a minimum statistical power of 80%. Assuming a mean of 0 LogMAR, a standard deviation of 0.10 (based on historical ACUVUE® OASYS®) and a correlation between eye of 0.80, 2000 replicating trials were simulated for the repeated measurements from the multivariate normal distribution.

Acceptable Lens Fit

Acceptable lens fit is a binary response as y=1 if a subject eye has an acceptable fit and 0 otherwise. The common reference rate of 95% was selected for the sample size calculation, since this is considered to be a more conservative reference proportion. Assuming a correlation 0.80 between measurements within the same subject and period; and assuming a correlation of 0.50 between measurements within the same subject across periods. A total of 2000 replicating trials were simulated to estimate a sample size with a minimum statistical power of 80%.

Slit Lamp Findings

There was no Grade 3 or higher SLFs in any of the four historical studies. Therefore an incidence rate of 0.5% was chosen based on previous research literature^{3, 4}. Assuming a correlation 0.50 between measurements within the same subject and period; and assuming a correlation of 0.30 between measurements within the same subject across periods. A total of 2000 replicating trials were simulated to estimate a sample size with a minimum statistical power of 80%.

Table 7: Sample Size Estimates and Power Calculations for Primary Endpoints

Endpoint	Number per Subjects to Complete	Power
Distance Monocular Visual Acuity	40	>99%
SLFs Grade 3 or Higher	120	86%
Acceptable lens Fit	70	83%
CLUE Comfort	60	80%

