14.4. Level of Statistical Significance

The primary and secondary hypotheses will be tested with a type I error of 5% individually.

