$$\text{Numerator} = \beta_0 + \beta_1 \text{Lens}_{i[j,k]} + \beta_3 \text{period}_{j1} + \beta_4 \text{period}_{j2} + \beta_5 \text{sequence}_k + \beta_6 \text{Carry1}_{i[j,k]} + \gamma_1 + \delta_{m(l)} + \alpha_{j(m(l))}$$

We assume the random subject eye effects are i.i.d as $\alpha_{j(m(l))} \sim N(0, \sigma_{\text{eye/subject/site}}^2)$ for eye nested within subject within clinical site, the random effect for subject are i.i.d as $\delta_{m(l)} \sim N(0, \sigma_{\text{subject/site}}^2)$ for subject nested within clinical site and the random clinical site effects are i.i.d as $\gamma_m \sim N(0, \sigma_{\text{site}}^2)$ for $i=1, 2$ (eye), $j=1, 2, 3$ (period) $k=1, 2$ (Sequence) $l=1, \dots, 5$ (Site) $m=1, \dots, n_l$ (subject/site).

For the β coefficients, independent non-informative priors $N(0, 10000)$ will be used. For the variance of random effects of $\sigma_{\text{eye/subject/site}}^2$, $\sigma_{\text{subject/site}}^2$ and σ_{site}^2 , independent non-informative conjugate priors inverse-gamma (0.001, 0.001) will be used. The Metropolis-Hastings algorithm as implemented in the SAS/STAT 14.1 PROC MCMC procedure will be used to estimate posterior distributions of the unknown parameters. Inferences will be made based on the posterior credible interval for the relevant parameters.

Hypothesis Testing

With respect to Acceptable lens fit the null and alternative hypothesis for superiority is as follows:

$$\begin{aligned} H_0 &= p \leq 0.90 \\ H_1 &= p > 0.90 \end{aligned}$$

Where, p represents the proportion of subject eyes that achieve acceptable fit for the Test lens.

Success for acceptable fit will be declared if the lower bound of the 2-sided 95% credible interval of the proportion is greater than 0.90; i.e. $P(P > 0.90) \geq .975$.

Primary safety analysis:

Slit Lamp Findings

Grade 3 or higher slit lamp findings will be analyzed using a Bayesian Logistic regression random-effects model to compare the Test and Control lenses. The regression model will include baseline slit lamp findings, lens type, period, sequence of lens wear and first order carryover effect. Site, subject nested within site and eye within subject within site will be included in the model as random effects.

Let $y_{ijklmn}=1$ if a Grade 3 or higher SLF is observed and $y_{ijklmn}=0$ otherwise for the n^{th} subject, from the m^{th} site, assigned to the i^{th} study lens for the j^{th} eye in the k^{th} period using the l^{th} sequence.

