$$Y_{ijklmn} \sim \text{Binary}(p_{ijklmn})$$

$$p_{ijklmn} = \frac{\exp(\text{Numerator})}{1 + \exp(\text{Numerator})}$$

$$\begin{aligned} \text{Numerator} = & \beta_0 + \beta_1 \text{Lens}_{ij[k,l]} + \beta_2 \text{Baseline SLF}_1 + \beta_3 \text{period}_{k1} + \beta_4 \text{period}_{k2} + \\ & \beta_5 \text{sequence}_k + \beta_6 \text{Carry1}_{i[k,l]} + \gamma_m + \delta_{n(m)} + \alpha_{j(n(m))} \end{aligned}$$

We assume the random subject eye effects are i.i.d as $\alpha_{j(n(m))} \sim N(0, \sigma_{\text{eye/subject/site}}^2)$ for eye nested within subject within clinical site, the random effect for subject are i.i.d as $\delta_{n(m)} \sim N(0, \sigma_{\text{subject/site}}^2)$ for subject nested within clinical site and the random clinical site effects are i.i.d as $\gamma_m \sim N(0, \sigma_{\text{site}}^2)$ for $i=1,2$ (lens), $j=1, 2$ (eye) , $k=1, 2, 3$ (period) $l=1, 2$ (Sequence) $m=1, \dots, 5$ (Site) $m=1, \dots, n_m$ (subject/site).

In this model, the lens I will be determined by the period k and sequence l , therefore i is denoted as a function of j and k . We define $\text{Lens}_i=0$ for the Control lens and $\text{Lens}_i=1$ for the Test lens.

For the β coefficients, independent non-informative priors $N(0, 10000)$ will be used. For the variance of random effects of $\sigma_{\text{eye/subject/site}}^2$, $\sigma_{\text{subject/site}}^2$ and σ_{site}^2 , independent non-informative conjugate priors inverse-gamma (0.001, 0.001) will be used. The Metropolis-Hastings algorithm as implemented in the SAS/STAT 14.1 PROC MCMC procedure will be used to estimate posterior distributions of the unknown parameters. Inferences will be made based on the posterior credible interval for the relevant parameters.

Hypothesis Testing

The null and alternative hypothesis for Non-inferiority is as follows:

$$H_0: p = (p_{\text{Test}} - p_{\text{Control}}) \geq 0.05$$

$$H_A: p = (p_{Test} - p_{Control}) < 0.05$$

Where p represents the difference between the proportion of subject's eyes with Grade 3 or higher SLFs of the test group compare to the control group. Non-inferiority will be established if the upper limit of the 2-sided 95% credible interval is below 0.05, i.e. $P(p=p_{Test} - p_{Control} < 0.05 | y)=0.975$.

In the event that the number of Grade 3 or higher SLFs is too small Grade 2 or higher SLFs will be analyzed and tested as described above.

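### The slit lamp and acuity models in section 14.5 omit a subject-by-period effect, so they cannot carry the extra same-period correlation between fellow eyes that the plan itself assumes for slit lamp findings

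*Combined protocol and SAP*

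**What the plan says.** Under section 5.1 lenses are worn bilaterally, in the sequence Test/Control/Control or Control/Test/Test. A subject's two eyes therefore always wear the same lens in a given period.

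For visual acuity, section 14.5 says "Clinical site and subject nested within clinical site will be included as random effects". The equations that follow also contain a random eye effect within subject, and a 3x3 covariance matrix over the three periods of one eye. For slit lamp findings it says "Site, subject nested within site and eye within subject within site will be included in the model as random effects". No term in either model is shared by a subject's two eyes in one period only.

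Section 14.2 gives the correlations used for sizing:
- slit lamp findings: "correlation 0.50 between measurements within the same subject and period; and assuming a correlation of 0.30 between measurements within the same subject across periods";
- lens fit: "Assuming a correlation 0.80 between measurements within the same subject and period; and assuming a correlation of 0.50 between" periods;
- acuity: "a correlation between eye of 0.80", with no across-period value.

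Section 14.4 says "The primary and secondary hypotheses will be tested with a type I error of 5% individually". Section 14.5 applies this as a posterior probability of 0.975, so the one-sided benchmark is 2.5%. For slit lamp findings "Non-inferiority will be established if the upper limit of the 2-sided 95% credible interval is below 0.05". For acuity, section 2.3 says "A non-inferiority margin of 0.05 logMAR and a superiority margin of 0 logMAR will be used". If Grade 3+ findings are too few, section 14.5 moves to Grade 2+ with the same model and test.

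**The concern.** With bilateral wear the lens effect is a contrast between periods within a subject. Site, subject and eye effects are constant over periods, so in a linear model they drop out of that contrast. What remains for each eye is its period-to-period variation, which the models take as unrelated between fellow eyes. If the eyes move together from period to period (a common visit, examiner, refit or tear-film state), two correlated contrasts are counted as two independent ones and the interval for the lens difference is too narrow.

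The plan expects such movement for slit lamp findings: its sizing correlation is higher within a period than across periods. At stake are the error rates of the slit lamp non-inferiority test, its Grade 2+ fallback, and the acuity non-inferiority and superiority tests.

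**Working it through.** **Estimator.** Take one lens effect with sequence, period and first-order carryover. Let d1, d2, d3 be the between-sequence differences in mean outcome by period. The lens estimate is d1/2 − (d2 + d3)/4. The squared weights sum to 0.25 + 0.0625 + 0.0625 = 0.375, so

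Var = 0.375 × 2 × v/(N/2),

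where N is the number of completers and v is the period-specific variance of a subject's two-eye mean. With same-period fellow-eye correlation w and one across-period correlation a for all pairs:
- true v = s²[(1 + w)/2 − a];
- v without a subject-by-period term = s²(1 − a)/2;
- true/model variance ratio = 1 + (w − a)/(1 − a).

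**The plan's own power figures (Table 7).** Power = Φ(margin/SE − 1.96).
- Acuity, above 99% at 40 completers (SD 0.10, w = 0.80): this gives 98.3% at a = 0.5, 99.7% at a = 0.6 and above 99.9% at a = 0.8. The stated figure needs a of about 0.6 or more.
- Slit lamp, 86% at 120 completers: this does not reproduce. With a 0.5% rate, 0.50/0.30 and a 5-point margin, SE is 0.53 points and power exceeds 99.9%. The simulation behind the 86% is not described, so this is a query to the sponsor; nothing below depends on it.

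**Slit lamp findings** (w = 0.50, a = 0.30, N = 120).
- Variance ratio 1 + 0.20/0.70 = 1.286; SE ratio √1.286 = 1.134.
- SE understated by 1 − 1/1.134 = 11.8%.
- One-sided error P(Z > 1.96/1.134) = 4.2%; coverage of the nominal 95% interval 91.6%.
- At 0.5%, s² = 0.005 × 0.995 = 0.004975. True SE = √(0.0125 × 0.004975 × 0.45) = 0.53 points; model SE = √(0.0125 × 0.004975 × 0.35) = 0.47 points. At zero observed difference the upper limit is 1.04% rather than 0.91%, against 5%.

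The Grade 2+ rate is not legible in the documents, so the rates below are assumed. True difference is zero and N = 120.

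| Grade 2+ rate | True SE (points) | Power from true SE | Power implied by model SE |
|---|---|---|---|
| 2% | 1.05 | 99.8% | above 99.9% |
| 5% | 1.63 | 86.4% | 93.4% |
| 10% | 2.25 | 60.3% | 71.2% |
| 20% | 3.00 | 38.5% | 47.2% |

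As a check on the linear formula, binary data with 0.50/0.30 correlations were simulated (250 trials per rate) and fitted by maximum likelihood with a logistic model holding a random subject intercept and no subject-by-period term. The SE ratio was 1.19 at a 10% rate and 1.12 at 20%, with coverage 91.6% and 93.6%. This fit left out site, eye and baseline terms and did not use the plan's priors.

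**Acuity** (w = 0.80, SD 0.10, N = 120; a is an assumption).

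| a | True SE | Model SE | Ratio | One-sided error |
|---|---|---|---|---|
| 0.8 | 0.0035 | 0.0035 | 1.00 | 2.5% |
| 0.7 | 0.0050 | 0.0043 | 1.15 | 4.5% |
| 0.6 | 0.0061 | 0.0050 | 1.22 | 5.5% |
| 0.5 | 0.0071 | 0.0056 | 1.26 | 6.1% |

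Non-inferiority power at N = 120 from the true SE is at least 99.7% even at a = 0.

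**Condition on the acuity table.** It assumes an estimable lens effect. The written acuity means have eight free parameters (intercept, two period, three lens, sequence, carryover) for six sequence-by-period means. The design has rank 6, and adding the tested contrast (β1 + β2 + β3)/3 raises it to 7, so that contrast is not identified. With the N(0, 1000) prior read as a variance, its posterior SD is about 11 to 13 logMAR at any sample size, depending on the prior given to the intercept and period effects.

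**The case against.** **Fellow eyes are not treated as independent outright.** A reader might infer that they are. They share site and subject effects and so are marginally correlated in both models. Independence holds only given the subject and eye effects; what is missing is extra correlation within a period. This stands.

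**Acuity has no stated across-period correlation.** It is tempting to take the lens-fit pair, 0.80 and 0.50, and report an acuity variance understated by a factor of 1.6. Those inputs belong to another endpoint. If the acuity value is 0.80, nothing is understated. This stands; only the range can be given.

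**As written, the acuity interval is not too narrow.** The unidentified contrast makes it prior-driven and far too wide for a 0.05 margin. This also stands. The understatement arises only after recoding, and adding a variance component alone would not repair the acuity test.

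**The plan does not say that its same-period correlation refers to fellow eyes.** It could refer to repeat visits. This is weaker: the slit lamp response is indexed by eye and period, and periods 2 and 3 each have one scheduled follow-up visit, so the scheduled same-period pair there is the two eyes.

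**The slit lamp model is logistic, so subject effects do not simply cancel.** True; 1.13 is an approximation. The simulations support its size at 10% and 20%, but were not run at 0.5%.

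**Decisions would hardly change.** For Grade 3+ findings and acuity non-inferiority at zero true difference this stands, and the error rates quoted for non-inferiority apply only when the true difference sits at the margin. It does not cover the Grade 2+ fallback, or acuity superiority, where the reference value is zero.

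**Section 14.3 says that a separate SAP supersedes these sections.** No such text is in the documents reviewed, so a correction there can be neither confirmed nor excluded.

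**Conclusion.** The omission is real in both models, and for slit lamp findings it conflicts with the plan's own sizing inputs. There the lens-difference SE is about 12% too small and one-sided error about 4.2% instead of 2.5%. This rests on 0.50/0.30 describing fellow eyes, one across-period correlation for same-eye and fellow-eye pairs, and a linear approximation. It is of little consequence for Grade 3+ findings at 0.5%. It can matter for the Grade 2+ fallback, which is a realistic prospect: section 14.2 reports no Grade 3+ finding in four historical studies.

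For acuity, the SE ratio lies between 1.00 and 1.26 for across-period correlations from 0.8 down to 0.5, conditional on first making the lens contrast estimable. The practical exposure is the superiority claim.

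A reader might conclude that the two primary non-inferiority results would be unsafe. The figures do not support that at the plan's assumed zero difference. Severity: should-fix.

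The fit model has the same gap (0.80 against 0.50), but it tests a one-lens proportion and is not part of this point.

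**What to change.** - **Acuity:** analyse the mean of the two eyes per subject and period, with the 3x3 covariance matrix at subject level and random site only, as the comfort model already does. Alternatively, keep eye-level data and add a random subject-by-period effect nested in site. Separately, recode the lens, sequence and carryover terms so that the tested contrast is estimable; neither change replaces the other.
- **Slit lamp findings:** add a random subject-by-period effect to the logistic model, and state that it also applies to the Grade 2+ fallback.
- **Sizing:** state the across-period correlation assumed for acuity, and say that the same-period correlation refers to fellow eyes.

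**Cost.** Intervals widen slightly. Acuity non-inferiority power at 120 completers stays at or above 99.7%. For a Grade 2+ fallback, honest power is lower than the present model suggests, for example 86.4% against 93.4% at an assumed 5% rate. At 0.5%, 120 × 2 × 3 = 720 eye-periods give about 3.6 expected Grade 3+ events, so the added variance component will depend on its prior. Prespecify that prior and report results under at least one alternative. The change is confined to the analysis specification and should be made before database lock.
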